Proprioceptive neuromuscular facilitation (PNF) are synergistic pattern of movement with the emphasis of facilitating normal movement, the proposed mechanism for some types of PNF that they are reliant on the facilitation of golgi tendon organs and muscle spindles which are responsible for two reflexes 1. autogenic inhibition 2. Reciprocal inhibition, although there is conflicting evidence regarding the mechanisms of PNF the beneficial effects are well established on many conditions like range of motion, neuromuscular functions, lymphedema and many more.

Most of the studies that tested PNF on the cervical region measured range of motion, flexibility and strength. Studies conducted to influence cervical proprioception used multiple interventions such as head relocation practice, eye/head coordination exercises, muscle vibration, mental training, strength and motor control exercises.

Due to the importance of cervical proprioception and the lack of studies in literature, the Purpose of this study is to investigate the acute influence of proprioceptive neuromuscular facilitation on cervical proprioception, range of motion and strength.

Study Design: This is a double-blinded randomized controlled trial. Participants were not aware of their assigned group, also the assessor was blinded to group allocation.

Sample Size: The sample size was calculated by using G*Power 3.1.7 for Windows (G*Power©, University of Dusseldorf, Germany), by using f family test ANOVA repeated measures and between factors, with statistical power of 0.80 (1-B error Probability) and alpha error level probability of 0.05 and effect size of 0.25 with number of measurements being 2, which total to 120 participants.

Participants will be recruited from university campus by directly asking students from classes if they can volunteer by explaining that the trial will involve the cervical region, also mentioned that is one-time session that can take up to an hour. Participants then will be handed consent forms that included more details about the trial.

Inclusion Criteria:

- Neck disability index score of 5 or less
- Able to understand and follow instructions
- Above 18 years old

Exclusion Criteria:

- Cervical trauma
- History of cervical inter-vertebral disc pathology
- Rheumatic diseases
- Whiplash syndrome
- History of surgeries to the neck, face and shoulders
- History of systemic diseases

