Randomization and Procedures Randomization done by a person external to the study. Participants that signed the consent form and meet the inclusion criteria were assigned a number which corresponded to one of the three groups. Participants were asked to enter a room where the assessor performed the first measurements, then participants were asked to go to a separate room where the treatment methods took place. The therapist corresponded the number of the participant to the randomization sheet and applied the assigned treatment. After that participants were asked to go back to the first room for the second measurement. Participants were asked not to make a comment to the assessor but they can direct any question to the therapist.

ASSESSMENT METHODS

Cervical Proprioception: The cervical proprioception will be done using cervical range of motion instrument (CROM, Performance Attainment Associates, Lindstrom, MN, USA) using the joint position accuracy method of proprioception assessment, the device is made of a plastic frame that rest over the head, nose and ears, with a strap to secure it, it has three inclinometers attached to the frame, one in the sagittal plane, the second in the frontal plane and the third in the horizontal plane, which makes able to measure all 6 directions of movement. This instrument was reliable and valid to assess cervical proprioception, the chosen target angle is 30 degrees.

Cervical proprioception was done for flexion, extension, right side bending, left side bending, right and left rotation.

Participants will be asked to sit and put on the CROM instrument, then they will be instructed to start moving their head to one of directions then the assessor will stop them at 30 degrees and tell them to feel the amount of movement and muscle tension, this will be repeated 3 times as a reference, then they will be asked to do the movement with the eyes closed until they reach the target angle, this will be repeated for 3 times, this will be done for each direction and the assessor will record the results.

Range of Motion and Muscle Strength Measurement:

Active Range of motion (AROM) will be measured using CROM instrument, the validity and reliability of CROM to assess ROM is well documented in the literature, AROM was taken for all movement directions.

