Statistical analyses will be performed using SPSS software version 25. Descriptive analyses will be presented using means and standard deviations for continuous data and frequencies and percentages for categorical data. The variables investigated using Kolmogorov Smirnov test to determine whether or not they are normally distributed. Since the variables are normally distributed, ANOVA will be used to compare the means of the groups., Levene test will be used to assess homogeneity of variances. When an overall significance will be observed, pairwise post-hoc tests will be performed using Tukey's test. Since the variables are not normally distributed Kruskal-Wallis test will be used to compare the groups. The Mann-Whitney U test will be performed to test the significance of pairwise differences using Bonferroni correction to adjust for multiple comparisons. Since the variables are normally distributed, the effect of time change in measurements will be investigated by Repeated Measures ANOVA test. Greenhouse-Geisser correction will be used when sphericity assumption is violated. Since the variables are not normally distributed Friedman test will be used. The Wilcoxon test will be performed to test the significance of pairwise differences using Bonferroni correction to adjust for multiple comparisons. A 5% type-I error level was used to infer a statistical significance.

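### The between-arm ANOVA specifies neither the value analysed nor any baseline adjustment, although measurements are taken before and after treatment

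*Combined protocol and SAP*

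**What the plan says.** The same statistical text stands in the study summary table (Statistical Methodology) and in the Statistical Analysis Plan section. For the arms it says "ANOVA will be used to compare the means of the groups", followed by Tukey comparisons. If the data are not normal, "Kruskal-Wallis test will be used to compare the groups", followed by Mann-Whitney tests with Bonferroni correction. Neither sentence names a time point, a change score or a covariate.

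The pre/post pair enters in a separate sentence: "the effect of time change in measurements will be investigated by Repeated Measures ANOVA test". The non-normal counterpart reads "Since the variables are not normally distributed Friedman test will be used", followed by Wilcoxon tests. No arm factor or arm-by-time term is mentioned.

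Under Randomization and Procedures, "Participants were asked to enter a room where the assessor performed the first measurements". Treatment follows in a separate room, and "After that participants were asked to go back to the first room for the second measurement". That every outcome is measured on both occasions is a fair inference, but it is not stated.

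The Sample Size paragraph was calculated "by using f family test ANOVA repeated measures and between factors", with power 0.80, alpha 0.05 and "effect size of 0.25 with number of measurements being 2, which total to 120 participants". It gives no pre-post correlation and does not say which difference the effect size describes.

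**The concern.** The trial is randomised against a control, so the comparison between arms is its answer. As worded, an ANOVA of post-treatment values and an ANOVA of changes both comply with the plan, and they can disagree on the same data. Each keeps its type I error if fixed in advance. Choosing between them after seeing results does not.

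Precision is also at stake. A pre-treatment measurement is collected from each participant, and the plan does not say how, or whether, it enters the between-arm estimate. Adjusting for it costs one degree of freedom and, if baseline and post-treatment values are at least moderately correlated, narrows the confidence intervals.

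**Working it through.** **Inputs.** From the documents: 3 arms, N = 120, 2 measurements, f = 0.25, alpha 0.05, power 0.80. Assumed, because not given: 40 per arm, equal pre and post SD, pre-post correlation ρ = 0.3 / 0.5 / 0.7, and arms that differ only after treatment.

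**1. Reproducing N = 120.** For the between factor of a repeated-measures ANOVA with m = 2, the noncentrality is λ = f²·N·m / (1 + (m − 1)ρ), with 2 and N − 3 degrees of freedom. At ρ = 0.5, λ = 0.0625 × 120 × 2 / 1.5 = 10.0 and power is 0.805; N = 117 gives 0.794. So 120 is reproduced. At ρ = 0.3 and 0.7 the same formula gives 105 and 135, and exactly 120 results for ρ from 0.48 to 0.51. The group-by-time interaction on the same scale, λ = f²·N·2 / (1 − ρ), needs only 60 / 42 / 27. Of the two repeated-measures tests, the stated N therefore matches the group effect averaged over the two occasions.

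**2. Interval width, which does not depend on the effect size.** The half-width of a Tukey-adjusted 95% CI for a pairwise difference, in SD units, is 2.374 × √(2/40) × k = 0.531 × k. Here k = 1 for the post value, √(2(1 − ρ)) for change and √(1 − ρ²) for ANCOVA. The small term for chance baseline imbalance is ignored.

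| Analysis | ρ = 0.3 | ρ = 0.5 | ρ = 0.7 |
|---|---|---|---|
| Post-only | 0.53 | 0.53 | 0.53 |
| Change | 0.63 | 0.53 | 0.41 |
| ANCOVA | 0.51 | 0.46 | 0.38 |

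ANCOVA with 120 participants is worth a post-only trial of 120 / (1 − ρ²) = 132 / 160 / 235. At ρ = 0.1 the ANCOVA half-width is 0.531 × √0.99 = 0.528, so there is practically no gain.

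**3. Power if f = 0.25 is the post-treatment difference.** Let L = 0.0625 × 120 = 7.5. Then λ is L for post-only, L / (2(1 − ρ)) = 5.36 / 7.50 / 12.50 for change, and L / (1 − ρ²) = 8.24 / 10.00 / 14.71 for ANCOVA (116 error degrees of freedom instead of 117).

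| Analysis | ρ = 0.3 | ρ = 0.5 | ρ = 0.7 |
|---|---|---|---|
| Post-only | 0.68 | 0.68 | 0.68 |
| Change | 0.52 | 0.68 | 0.89 |
| ANCOVA | 0.72 | 0.80 | 0.93 |

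At ρ = 0 or 0.1, ANCOVA power is 0.676 or 0.680, against 0.676 for post-only.

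**4. Power if f = 0.25 is on the averaged mean, the scale that reproduces 120.** With no arm difference before treatment, averaging halves the post-treatment difference, so the post-treatment f is 0.50 and L = 0.25 × 120 = 30. Power is then 0.999 for post-only, 0.988 / 0.999 / 1.000 for change and 1.000 throughout for ANCOVA.

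**5. Does the open choice matter?** In a simulation (10,000 trials per setting, 40 per arm, f = 0.25 on the post value), post-only and change-score ANOVA reached different verdicts at the 5% level in 32% / 30% / 32% of trials at ρ = 0.3 / 0.5 / 0.7. With no true effect and ρ = 0.5 they differed in 8%, although each test alone rejected in about 5%.

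**The case against.** The strongest defence is that the plan may already intend a mixed model. It was sized on a repeated-measures design with a between factor, and with two occasions the group-by-time test of such a model is the same as an ANOVA of change. That is plausible, but the SAP ties its repeated-measures ANOVA to time alone and never links it to the arms, and Friedman and Wilcoxon tests have no between-arm term.

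It can also be said that ANCOVA is a preference among valid methods and that its benefit rests on an unknown correlation, which may differ between outcomes and directions. This stands: the gain is small at 0.3 and negligible near zero.

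Three stronger readings are tempting, and the documents do not support them:

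- *The ANOVA ignores baseline.* The analysed value is not named, so a change-score ANOVA, which uses baseline, cannot be excluded. What can be shown is silence, not non-use.
- *The trial is underpowered, at 0.68.* That figure requires f = 0.25 to describe the post-treatment value, which the Sample Size paragraph does not say. On the scale that reproduces 120, post-only, change and ANCOVA all have power of at least 0.98.
- *The arms will be compared on the average of pre and post.* If f = 0.25 were the post-treatment difference, that test would have power of only 0.30 / 0.27 / 0.24. But the SAP does not name it as the between-arm test, so these figures are a reason to exclude it, not a finding about the planned analysis.

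**Conclusion.** The point holds as a gap in pre-specification with an inexpensive gain in precision. It should be fixed, but it is not a source of bias: a post-value or change-score ANOVA fixed in advance would be valid in randomised arms. The omission itself is certain from the text; the size of the benefit is conditional. Under the assumptions above, ANCOVA narrows the pairwise interval from 0.53 SD (post-only) to 0.51 / 0.46 / 0.38 SD, and it also beats change scores at each correlation examined. Power improves materially only if f = 0.25 refers to the post-treatment difference. If it refers to the averaged mean, power is near its maximum under all three analyses and the benefit lies in interval width alone.

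**What to change.** In the study summary table and the Statistical Analysis Plan section, state:

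- The single between-arm analysis of each outcome is an ANCOVA of the post-intervention value on arm (three levels), with the baseline value of the same outcome as covariate.
- Adjusted pairwise differences are reported with Tukey-type or Bonferroni-adjusted 95% CIs.
- Tests of time within arms are descriptive, and the group effect averaged over pre and post is not used as the between-arm test.
- A baseline-adjusted rank ANCOVA may be given as a sensitivity analysis, in place of the unadjusted Kruskal-Wallis test.

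In the Sample Size paragraph, keep N = 120, state which difference f = 0.25 refers to and which correlation is assumed, and report ANCOVA power over a range of correlations. If f = 0.25 is on the post-treatment value, that is 0.72 / 0.80 / 0.93 at 0.3 / 0.5 / 0.7. A range is preferable to one correlation picked because it returns 0.80.

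The cost is revised wording in three places and one error degree of freedom (117 to 116). It needs no added participants, visits or measurements. On the post-treatment reading with a correlation of 0.3, power would be below the 0.80 target, and the text should say so.

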YEDITEPE UNIVERSITY

STUDY PROTOCOL AND STATISTICAL ANALYSIS PLAN

The Acute Influence of Proprioceptive Neuromuscular
Facilitation on Cervical Proprioception and Range of Motion.

Date: 25/02/2019

NCT Number:
NCT04045106

Prepared by:

[name]

ISTANBUL/TURKEY

Study Summery

Title	The acute influence of Proprioceptive neuromuscular facilitation on cervical proprioception and range of motion.
Methodology	Randomized, controlled trial, double blinded study
Study Duration	The estimated time for participants recruitment, screening and protocol implantation is 20 days
Study Location	University Labs
Subjects	120 healthy subjects randomized to 3 arms: 2 treatment and 1 control Inclusion criteria: To determine if a participant is healthy a score of 5 or less on the neck disability index will be used, no history of cervical trauma, rheumatic diseases, whiplash syndrome, no history of surgeries to the neck, face and shoulders, no history of cancer, no history of systemic diseases, age of 18 or above and able to understand and follow instructions.
Assessment	Cervical Proprioception using cervical range of motion (CROM) instrument, Active Range of motion (AROM) using CROM instrument, Muscle strength using a myometer device.
Intervention	PNF Pattern: Dynamic of reversals technique, PNF stretching: contract-relax-antagonist contract (CRAC) technique, control group: ineffective passive ROM.

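### Holm's method dominates the planned single-step Bonferroni for the three Mann-Whitney comparisons: about 3 to 7 points more power at the same per-outcome 5% level, by wording alone

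*Combined protocol and SAP*

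**What the plan says.** The study summary sets the design: "120 healthy subjects randomized to 3 arms: 2 treatment and 1 control". The Statistical Analysis Plan, repeated in the Statistical Methodology row of the summary, gives two routes for comparing the groups.

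- **Normal data:** ANOVA, and then "When an overall significance will be observed, pairwise post-hoc tests will be performed using" Tukey's method. Here the overall test is written as a condition for the pairwise step.
- **Non-normal data:** Kruskal-Wallis, and then "The Mann-Whitney U test will be performed to test the significance of pairwise differences using Bonferroni correction". No condition on the Kruskal-Wallis result is written, and neither the number of comparisons nor the divisor is given.

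The level is fixed by "A 5% type-I error level was used to infer a statistical significance". No stepwise procedure is named. The Sample Size paragraph powers an overall test and gives no power for any pair of arms.

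**The concern.** The trial asks whether either form of PNF does better than ineffective passive movement, so the two PNF-versus-control comparisons carry the answer. On the rank route each comparison must reach 0.0167 regardless of how the other two turn out. Single-step Bonferroni ignores the fact that once one of the three null hypotheses has been rejected, at most two remain to be protected. A step-down method uses that fact. At stake is some pairwise power that the plan could keep at its own stated error level, with the same participants and measurements.

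**Working it through.** **Inputs from the documents.** Three arms; "alpha error level probability of 0.05"; "with statistical power of 0.80 (1-B error Probability"); "effect size of 0.25 with number of measurements being 2, which total to 120 participants"; test family "f family test ANOVA repeated measures and between factors".

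**Assumptions.** Equal allocation (40 per arm), no dropout, correlation 0.5 between the two measurements, two-sided pairwise tests, three pairs in the Bonferroni divisor, normal data with equal spread.

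**1. The plan's own figure.** The noncentrality is λ = f²·N·m / [1 + (m − 1)ρ] = 0.0625 × 120 × 2 / 1.5 = 10.0, with 2 and 117 degrees of freedom. Power is 0.805, and 120 is the smallest total with equal arms that reaches 0.80. The stated 120 therefore reproduces at ρ = 0.5.

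**2. The effect size as a distance between arms.** If one arm differs from two equal arms by d standard deviations, the SD of the three means is d√2/3, so d = 3f/√2.

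- Single measurement: d = 3 × 0.25/√2 = 0.53.
- Average of two measurements at ρ = 0.5: f becomes 0.25/√0.75 = 0.289, so d = 0.612. This is the scale on which 120 gives 80% power.

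The plan does not say which quantity enters the rank tests, so both values are carried.

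**3. The thresholds.** Order the three p-values from smallest to largest.

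- Bonferroni compares each with 0.05/3 = 0.0167.
- Holm compares them in turn with 0.05/3 = 0.0167, 0.05/2 = 0.025 and 0.05, and stops at the first failure.

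Every Holm threshold is at least as large as Bonferroni's, so Holm rejects everything that Bonferroni rejects. The smallest p-value faces the same threshold in both, so they reject at least one pair in exactly the same trials. Holm's familywise control rests on the same inequality as Bonferroni's, so it needs nothing further.

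**4. Power by simulation** (rank route, pairs tested after a significant Kruskal-Wallis test):

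| Truth | Claim | Bonferroni | Holm |
|---|---|---|---|
| One PNF arm differs by 0.53 SD | that arm vs control | 0.44 | 0.47 |
| Both PNF arms differ by 0.53 SD | both vs control | 0.28 | 0.33–0.34 |
| One PNF arm differs by 0.612 SD | that arm vs control | 0.58 | 0.62 |
| Both PNF arms differ by 0.612 SD | both vs control | 0.42 | 0.49 |

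The range in the second row is variation between simulation runs. Dropping the Kruskal-Wallis condition changes the one-pair figures by less than half a point and leaves the gains as they are.

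**5. Familywise error by simulation.** With all arms equal, Bonferroni and Holm agree, as step 3 requires: 4.3% without a Kruskal-Wallis condition and 4.0% with one. With two arms equal and the third far away, Bonferroni gives 1.7%. Holm then tests the remaining pair at its full 5%, and simulation gives 5.0% to 5.2%.

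**The case against.** Bonferroni-corrected Mann-Whitney tests are valid and conservative, and nothing in the documents contradicts them. That stands: this is a matter of efficiency. Four stronger readings are tempting, and the documents do not support them.

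- **The plan spends only a third of its 5%.** This is true only when exactly one pair is truly equal (1.7%). With all arms equal the pairwise step spends about 4%.
- **The correction costs about 10 points of power.** That figure compares Tukey or Bonferroni with a closed test (overall test at 5%, then each pair at 5%). The loss runs from about 3 points (extreme pair of evenly spaced means) to about 14 (adjacent pairs).
- **Pairwise power is already 50% or less at the planned effect.** This uses 0.53 SD. At 0.612 SD, which matches the stated sample size, it is 58% (Mann-Whitney with Bonferroni) to 64% (Tukey).
- **Both corrections should give way to the closed test.** For three arms it is legitimate: at 0.53 SD it gives 0.55 for one pair and about 0.45 for both PNF arms. But the rank route states no Kruskal-Wallis condition, and unadjusted pairs without one give about 12% familywise error. It also gives up simultaneous intervals, and its error rose to about 6% in the rank route when spreads differed. It is a choice, not a correction. Nor does Holm's advantage over Bonferroni say anything against Tukey.

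Two objections reach Holm as well. With unequal spreads and one arm far away, its error for equal centres was 5.9% to 6.5%. This arises because Mann-Whitney tests equality of distributions, not of centres; Bonferroni's smaller threshold only masks it. Second, six directions on three measures make 18 outcomes, with no primary and no correction across them. If one pair were equal throughout and outcomes were independent, the chance of at least one false pairwise claim would be 1 − 0.983^18 ≈ 27% at 1.7% each and 1 − 0.95^18 ≈ 60% at 5% each, the most that Holm can nominally reach. That problem is real but separate. A correction over three pairs does not address it, and it is no reason to keep a dominated method within an outcome.

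**Conclusion.** The point holds as a free improvement on the non-normal route. Holm dominates single-step Bonferroni at the same nominal 5% familywise level per outcome. The gain is 3 to 4 points for one PNF-versus-control comparison and about 5 to 7 points for detecting both PNF arms. The dominance follows from the thresholds and rests on no assumption about the data. The sizes rest on 40 per arm, three comparisons and normal data with equal spread, and the 0.612 SD figures also on a correlation of 0.5. The Tukey step is unaffected, and nothing here shows that the planned analysis is invalid.

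**What to change.** In the Statistical Analysis Plan and in the Statistical Methodology row of the summary, name Holm's correction instead of Bonferroni's in the Mann-Whitney sentence, and state that it covers the three pairs of arms within each outcome. Edit only that sentence; the separate Wilcoxon sentence on change over time also mentions Bonferroni and is not part of this point. Holm needs no significant Kruskal-Wallis result first. Add that the 5% control is per outcome and does not extend across outcomes.

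The cost is one changed term in two places, with no change to participants, measurements or level. If the sponsor prefers the closed test, the Kruskal-Wallis condition must first be written into that route, and confidence intervals shown beside the pairwise tests must be labelled individual rather than simultaneous.

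### The SAP tests change over time without a group-by-time contrast and does not say which test decides the PNF effect, so a gain from repeating the position test could be read as a PNF effect

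*Combined protocol and SAP*

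**What the plan says.** **Analysis.** The Statistical Analysis Plan, repeated in the Statistical Methodology row of the study summary, sets out two families of test side by side.

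- Between groups: "ANOVA will be used to compare the means of the groups", with Tukey post-hoc tests, or Kruskal-Wallis with Bonferroni-corrected Mann-Whitney tests. The plan does not say whether these use post-treatment values or changes.
- Over time: "the effect of time change in measurements will be investigated by Repeated Measures ANOVA test". Otherwise, "Since the variables are not normally distributed Friedman test will be used", followed by Bonferroni-corrected Wilcoxon tests.

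Both families are judged at 5%. No group-by-time term is named, and neither family is identified as the test of PNF.

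**Outcome.** Under Assessment Methods, Cervical Proprioception, the assessor stops the participant at 30 degrees to "tell them to feel the amount of movement and muscle tension, this will be repeated 3 times as a reference". The participant must then "do the movement with the eyes closed until they reach the target angle, this will be repeated for 3 times". The directions are listed: "Cervical proprioception was done for flexion, extension, right side bending, left side bending, right and left rotation". Randomization and Procedures puts one measurement before treatment and one after it. The recruitment text describes a single session of up to an hour.

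**Background.** "Studies conducted to influence cervical proprioception used multiple interventions such as head relocation practice", among other approaches.

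**The concern.** The stated purpose is causal: the acute influence of PNF. A test of time alone asks only whether the second measurement differs from the first. Anything that changes between the two contributes to it, including having just performed the same relocation task. The protocol itself lists relocation practice among the ways others have tried to influence this outcome, so the competing explanation comes from its own text. Friedman and Wilcoxon tests work within participants and cannot bring in the control arm. The repeated-measures ANOVA could do so, but only through an interaction that the plan does not name.

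At stake is the wording of the conclusion. As written, the plan leaves room to report a significant time effect, or a significant change in a PNF arm beside a non-significant one in the control arm, as evidence for PNF. Neither is a comparison of arms.

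**Working it through.** **1. The plan's own figure.** The Sample Size section gives a repeated-measures ANOVA, between factors, with f = 0.25, alpha 0.05, power 0.80 and 2 measurements, for a total of 120. With k = 3 groups, m = 2 measurements and correlation rho (not stated; 0.5 assumed):

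- Noncentrality = f² × N × m / (1 + (m − 1) × rho) = 0.0625 × 120 × 2 / 1.5 = 10, on 2 and 117 degrees of freedom.
- Power = 0.805. The smallest N is 119, or 120 in equal arms.

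The figure reproduces. It is powered for the group effect averaged over the two occasions, not for group-by-time.

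**2. Test exposure.** 6 directions × 3 reference movements = 18, and 6 × 3 eyes-closed attempts = 18, so 36 movements per assessment and 72 over the two.

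**3. Practice only, no PNF effect.** Assume 120 / 3 = 40 per arm (the allocation ratio is not stated) and the same gain d, in SDs of the change score, in every arm. Tests are two-sided at 5%.

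- One arm, paired t: noncentrality = d × √40, 39 degrees of freedom; rejection probability q.
- At least one of the two PNF arms significant: 1 − (1 − q)².
- At least one PNF arm significant and control not: [1 − (1 − q)²] × (1 − q).
- Pooled time test: noncentrality = 120 × d², on 1 and 117 degrees of freedom.

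| d | one arm: noncentrality | one arm: q | at least one PNF arm | PNF arm yes, control no | pooled: noncentrality | pooled time test |
|---|---|---|---|---|---|---|
| 0.2 | 1.26 | 0.235 | 0.41 | 0.32 | 4.8 | 0.58 |
| 0.3 | 1.90 | 0.457 | 0.70 | 0.38 | 10.8 | 0.90 |
| 0.5 | 3.16 | 0.869 | 0.98 | 0.13 | 30 | 1.00 |

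For example, at d = 0.3: 1 − 0.543² = 0.705, and 0.705 × 0.543 = 0.383.

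**4. Sensitivity to scale.** If the gain is instead measured in SDs of a single measurement, the one-arm noncentrality becomes d × √40 / √(2(1 − rho)). At rho = 0.5 the divisor is 1 and the table is unchanged. For d = 0.2, 0.3 and 0.5, q is 0.18, 0.35 and 0.74 at rho = 0.3, and 0.36, 0.67 and 0.98 at rho = 0.7.

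**5. Comparison of arms in the same scenario.** The expected change is d in every arm, so each between-arm difference in change is d − d = 0 and the group-by-time test keeps its level. Simulation (40,000 runs, rho = 0.5) gave rejection rates of 0.050 at d = 0.3 and 0.049 at d = 0.5. A between-group ANOVA on post-treatment values gave 0.052 and 0.050.

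**The case against.** The strongest reply is that the design already deals with practice. There is a randomised control arm given passive movement, participants and assessor are blinded, every arm takes the same two measurements, and a between-group test is planned. The sample size is built on the between-groups factor, which suggests that the group comparison is the important one. All of this stands. It limits the point to how the time tests are read. It does not remove it, because the SAP never says that only the group comparison counts.

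A reader might infer more than the documents support, in four ways.

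- **That the plan will claim PNF from separate tests in each arm.** It does not state per-arm testing, nor that the time test decides efficacy. It only leaves this open. The one-arm figures show what such a reading would risk.
- **That the baseline test is the practice intervention named in the Background.** The Background gives no dose, feedback or result for that intervention. Half of the 36 movements are guided references, and no error feedback is described on the eyes-closed attempts. The test resembles relocation practice in form; equivalence is not shown.
- **That participants would improve merely by repeating the test.** No passage says so, and fatigue could act the other way. In either direction the time test mixes a non-PNF change with PNF.
- **That the lack of a familiarisation run is a defect.** Guided reference movements already precede the eyes-closed attempts at both assessments. Once arms are compared, a rehearsal is not needed to remove a common gain.

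It is also fair to say that at a gain of 0.5 SD the control arm would itself be significant in 87% of trials, which would expose the practice effect to a careful reader.

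**Conclusion.** The point holds in a limited form. The time tests are planned as 5% inferential results with no control contrast, and the plan does not say which test decides the PNF effect. Read as evidence for PNF, with a practice-only gain of 0.2 to 0.5 SD of the change score, a single-arm test would mislead in about 24% to 87% of trials and the pooled time test in about 58% to 100%. Group-by-time stays near 5%.

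These figures assume 40 per arm, an equal gain in every arm, no PNF effect, a single outcome and approximately normal changes. The size of the gain is assumed, since the documents give none, so this is a possible error and not a measured one. The randomised comparison is not biased by a common gain, and the sample size is not affected. The change should be made because it governs what the trial can conclude about PNF.

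**What to change.** In the Statistical Analysis Plan, and in the matching summary row, state that:

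1. tests of time, pooled or within an arm, are descriptive only;
2. a PNF effect is claimed only from the between-arm comparison of change from first to second measurement, using group-by-time in the repeated-measures ANOVA or post-treatment values adjusted for baseline, with one of these chosen in advance;
3. for non-normal variables, the same claim rests on Kruskal-Wallis and Bonferroni-corrected Mann-Whitney tests applied to change scores.

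The cost is a few lines of text, with no added participants, measurements or session time. The one thing given up is the use of a significant pre-post change as evidence in its own right.

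I would not add a familiarisation run on this ground. It would lengthen a session that already holds two rounds of three outcomes plus treatment, and it would give everyone more relocation practice.
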